FRED HUTCHINSON CANCER RESEARCH CENTER

Current version: 10/18/2021

Version	1	7/24/2019
Version	2	2/27/2020
Version	3	09/10/2020
Version	4	04/20/2021
Version	5	09/21/2021
Version	6	10/18/2021

Title of Protocol:
Adaptation and Evaluation of an Online and eHealth Diet and Physical Activity Program to Improve Cardiometabolic Health in Rural Latino Adults "Mi Vida Saludable en el Valle"

Investigator List:		
[name]	Associate Professor, Fred Hutch	[contact]
Co-Investigators:		
[name], ND, PhD	Associate Professor, Fred Hutch	[contact]
Biostatistician:		
[name]	Professor, Fred Hutch	[contact]

SPONSOR: CCSG Pilot Funds (May 1, 2019 - December 31, 2021)

Additional Performance Sites:		
Site	Investigator	Phone Number
Center for Community Health Promotion	[name]	[contact]

Emergency (24-hour) phone number: office [contact], [contact]

PROTOCOL SYNOPSIS

Protocol Title	Adaptation and Evaluation of an In-person and eHealth Diet and Physical Activity Program to Improve Cardiometabolic Health in Rural Latino Adults “Mi Vida Saludable en el Valle”
Protocol Number	RG1005660
Protocol Sponsor	CCSG
Trial Phase	Phase 2
Trial Type	Pilot RCT
Clinical Indication	Latino adults with history of hypertension, diabetes, cardiovascular disease, cancer, or obesity
Study Objectives	
Aim 1 Assess feasibility of a remotely delivered and remotely assessed online group sessions and eHealth communication intervention strategies as measured by quantitative (accrual rate, intervention adherence, study retention, percent data collection processes completed, duration of staff assistance to complete data collection) and qualitative (exit interviews) data. Feasibility of intervention delivery for staff within the rural community context will be assessed and necessary adaptations from the urban intervention delivery process will be documented.
 
Aim 2 Examine changes from baseline to 3 months in nutrition and physical activity knowledge and preferences, and changes in physical activity patterns as assessed via Fitbit data.

Study Design	Feasibility study
Population	Latino residents of the Lower Yakima Valley with a history of hypertension, diabetes, cardiovascular disease, cancer, and/or obesity.
Primary Endpoints	Accrual rate, intervention adherence, study retention, data completion rates, assessability/acceptability (exit interview) and required intervention delivery adaptations.
Secondary Endpoints	Changes in nutrition and physical activity knowledge and preferences from baseline to 3 months. Changes in physical activity patterns as assessed via Fitbit data.
Type of control	N/A
Treatment Groups	Single-arm
Treatment Schedule	Participants will attend six 2-hour virtual nutrition and PA education sessions that include cooking and physical activity (i.e., dance class, walking in place). Participants will then receive 12 weeks of motivational text messages 4 times per week and link to access the nutrition cookforyourlife.org website. eHealth communication messaging will focus on increasing knowledge on the benefits of healthy nutrition, reducing intakes of energy dense and processed foods, and increasing physical activity.
Number of trial subjects	N=25
Estimated duration of trial	6 months
Duration of Participation	3-4 months

ABBREVIATIONS

CHE	Community Health Educator
-----	---------------------------

CCHP	Center for Community Health Promotion
IPAQ	International Physical Activity Questionnaire

Contents

1.0 GENERAL INFORMATION	5
1.1 Protocol Title	7
1.2 Sponsor Information	7
1.3 Investigator Information	7
2.0 INTRODUCTION TO THE PROTOCOL.....	7
2.1 Introduction	7
2.2 Background.....	8
2.3 Risks/Benefits	8
3.0 OVERVIEW OF CLINICAL TRIAL.....	8
3.1 Study Objectives.....	8
3.1.1 Primary Objectives.....	8
3.1.2 Secondary Objectives	8
3.2 Study Population	8
3.3 Study Design.....	9
3.3.1 Primary Endpoints	9
3.3.2 Secondary Endpoints	9
3.3.3 Exploratory Endpoints	9
3.4 Study Approach	9
3.5 Estimated Accrual.....	10
3.6 Name of Sponsor/Funding Source:.....	10
4.0 SUBJECT ELIGIBILITY	10
4.1 Inclusion Criteria.....	10
4.1.1 Demographic Data	10
4.1.2 Disease Related Criteria	10
4.1.3 Prior/Current Therapy Criteria	11
4.1.4 Accessibility Criteria	11
4.1.5 Clinical/Laboratory Criteria	11
4.1.6 Ability to understand and the willingness to sign an online informed consent document	12
5.0 SUBJECT REGISTRATION	12
6.0 STUDY PROCEDURES AND INTERVENTION.....	12
6.1 Informed Consent and Baseline Data Collection.....	13

6.2 Intervention Overview	14
6.3 Intervention Details.....	15
6.4 (eHealth Communication)	16
6.5 Activity Monitoring.....	16
6.6 Retention.....	16
6.7 Follow-up 3 Months Data Collection.....	17
7.0 SUBJECT EVALUATION	17
7.1 Evaluations	17
7.1.2 Retention calls and data collection.....	Error! Bookmark not defined.
8.0 SUBJECT DISCONTINUATION OF ACTIVE TREATMENT- WITHDRAWL.....	17
9.0 CONCOMITANT MEDICATIONS.....	17

1.0 GENERAL INFORMATION

This document is a clinical research protocol and the described study will be conducted in compliance with the IRB approved protocol, associated Federal regulations and all applicable IRB requirements. Pilot data collected from this feasibility study will support a novel R21 application to assess the efficacy of an online group sessions and eHealth communication intervention in a rural population of Latino adults with hypertension, diabetes, cardiovascular disease, cancer, and/or obesity via a feasibility assessment. Importantly, through collaboration with community partners, the current and subsequent trials will build community capacity to deliver nutrition and PA resources to underserved rural Latino adults and to introduce innovative technology-based intervention strategies not often applied in rural Latino communities.

Testing scalable intervention strategies for uptake of nutrition and PA recommendations as a new treatment model to improve cardiometabolic health with potential for broad dissemination among Latinos living in a rural community. This feasibility study will generate preliminary data needed to design a novel R21 proposal for a larger trial with long-term outcomes in a broad population of Latino adults living in a rural setting. We will leverage the Fred Hutch capacity and resources to provide rural adult Latinos with tools beyond brochures and single visit referrals to clinicians to discuss lifestyle modifications. This work has the potential to identify a scalable and cost-effective intervention targeting multiple lifestyle behaviors to be disseminated in clinical and community settings.

Building collaborations and new research opportunities. The proposed project maximizes strengths of 2 Fred Hutch Public Health Sciences investigators, Drs. [name] and [name], in a new collaboration and new research directions. [name] brings to the collaboration experience in community-based participatory research (CBPR) in rural Latino communities and [name] provides her expertise in behavioral nutrition and PA interventions among cancer survivors. This new collaborative project provides an opportunity for [name] to expand her research into rural Latino communities and [name] to gain experience in the fields of nutrition and PA intervention delivery, which sets the stage for future grant applications. Through current request of applications (RFAs), the National Cancer Institute (NCI)'s Division of Cancer Control and Population Sciences is currently highlighting and prioritizing the needs of rural communities, racial/ethnic populations, and obesity-related cancer prevention and control. Achieving the proposed project's specific aims will provide important pilot data on intervention adaptation, feasibility assessment, and preliminary effectiveness data needed to support a larger R01 grant application.

Community partnerships and capacity building. This project will develop new community collaborations among Latinos in the Lower Yakima Valley by adapting and developing the Mi Vida Saludable en el Valle intervention through partner feedback and interaction. Based on participant input, the intervention will be tailored to the unique nature and needs of this rural population with the goal of achieving a more effective intervention. Community partners will contribute to the delivery of the intervention by providing space and resources. Community partners, along with our Community Action Board (CAB), will receive information about data collection, research methods, and contribute to data interpretation and next steps towards an R21 application. These community partnerships contribute to the community's ability to evaluate and build capacity for future behavioral programs. A local chef and local community health educator will receive rigorous training to deliver the online group class intervention, which will ensure education and skills specific to nutrition and PA for rural Latinos remain in the community.

eHealth communication as a new strategy for nutrition and PA change in rural Latinos. The use of technology in behavioral interventions is proving to be a cost-effective way to deliver targeted nutrition and PA education to promote behavior change. Electronic (e) technology has been effective in many types of health interventions,

including smoking cessation¹ and diabetes management², among others.³⁻⁵ Studies suggest that when possible, participants should be offered multiple modes of theory-based e-communication to allow flexibility.^{6,7} However, there are limited data on the use of eHealth communication to achieve and maintain behavior change among Latino adults.

As part of the eHealth communication intervention, participants will receive weekly educational and motivational text messaging, and links to electronic (e) newsletters and a nutritional website. [name] has collaborated with the non-profit Cook for Your Life for the past decade on NCI funded R21 and R01 trials. The study will make use of the bilingual Cookforyourlife.org website, now owned by Fred Hutch, which is tailored to cancer survivors and is available in English and Spanish.^{7, 8} The website offers free nutrition and healthy cooking information, recipes, and cooking videos and disseminates scientifically supported information on nutrition and cancer survivorship. For the proposed trial, password-gated study specific pages will be created to provide resources addressing cancer, cardiovascular disease, diabetes and obesity.

Note about modifications due to the COVID-19 pandemic: On March 5, 2020, the Mi Vida Saludable en el Valle (My Healthy Life in the Valley) study among Latino cancer survivors was suspended due to the COVID-19 pandemic. Consenting for this study had not yet begun, but some recruitment activities had occurred, and interested individuals had provided their contact information to study staff. After consultation with IRO, these individuals were contacted and informed that the in-person intervention would be delayed due to public health related risk and that all consenting, and baseline data collection activities would be stopped immediately effective March 13, 2020. The intervention involved in-person group sessions with classroom education, cooking/eating, and exercise. Due to the foreseeable COVID-19-related risks of bringing immunosuppressed cancer survivors together for group activities, we have adapted our intervention and data collection activities to be delivered remotely. The trial has been modified to test an intervention that is remotely delivered and remotely assessed so that no part of the study or data collection procedures occur in groups or onsite at the Fred Hutch Center for Community Health Promotion office in Sunnyside, WA.

Although recruitment activities were able to resume under the modified, remote protocol and many recruitment methods were used, our staff were unable to enroll a significant number of Latino cancer survivors. In February 2021, Drs [name] and [name] reviewed the study and decided to expand the eligibility criteria to include Latinos with other conditions and chronic illnesses for which nutrition and PA lifestyle changes are recommended.³⁵⁻³⁶ This expanded the eligible population to include Latinos with hypertension, diabetes, cardiovascular disease, obesity, as well as Latino cancer survivors.

Modifications included modifications to the two arms of the study. The study was to use a high dose vs. low dose model for the study arms. The high dose arm would receive 6 virtual PA and nutrition classes every other week for 3 months. The low dose arm would receive 1 PA and nutrition class at the beginning of the intervention period. Both arms would have received the same set of eHealth materials including text message reminders and access to the Cook for Your Life website.

In October 2021, investigation into the reason for slow recruitment (n=22 to date) revealed a high burden of data collection for potential participants. In addition, preliminary analyses of data currently being collected by [name] in a similar intervention among a predominantly non-Hispanic white population of urban breast cancer survivors suggested a minimal effect of the low dose arm. As such, Drs. [name] and [name] decided to adapt the study as follows: change the design to be a single-arm feasibility study in which all participants receive the full “high-dose” intervention, decrease the target recruitment goal, and decrease participant burden by removing intensive data collection methods. These modifications will yield valuable information to determine how best to proceed with future diet and physical activity behavioral interventions in this rural population.

Overview of Study Design. The proposed pilot study will recruit 25 Latinos who are residents of the rural Lower Yakima Valley (LYV) with one or more of the following diagnoses based upon self-report: hypertension, diabetes, cardiovascular disease, obesity, or a history of cancer. Recruitment, retention, and data collection procedures will be carried out by Community Health Educator (CHE) study staff. Eligible participants will undergo online baseline assessments over a period of 1-2 weeks. Interested and eligible participants will be sent an online informed consent, HIPPA and medical records release form and baseline questionnaires to complete.

Following the completion of baseline data collection, participants will receive the intervention. All participants will receive a Fitbit device to self-monitor their PA. The intervention will include 6 biweekly 2-hour Zoom-based nutrition, culinary, and physical activity sessions. The sessions will be led by a local chef consultant and CHE, both trained by the study team. Participants will receive eHealth communication meant to motivate healthy diet and improved PA via educational and motivating text messages and using resources available as part of the study-related website over a 3-month period. Following completion of the 3-month intervention period, repeated baseline at-home assessments will take place and an exit intervention completed. The exit interview will include questions regarding acceptability and accessibility of the intervention for participants.

1.1 Protocol Title

Adaptation and Evaluation of an eHealth Diet and Physical Activity Program to Improve Cardiometabolic Health in Rural Latino Adults “Mi Vida Saludable en el Valle”

1.2 Sponsor Information

CCSG Pilot Funds (May 1, 2019 – December 31, 2021)

2.0 INTRODUCTION TO THE PROTOCOL

2.1 Introduction

The American Cancer Society and the American Institute for Cancer Research recommend cancer survivors to consume high-quality diets (i.e., diets high in fruits, vegetables, and whole grains, and low in energy-dense and processed foods) and to engage in ≥ 150 minutes per week of moderate-to-vigorous physical activity (MVPA).^{1, 2} The American Heart Association and American Diabetes Association have similar recommendations to promote cardiovascular health and improve the prevention or management of diabetes.³⁵⁻³⁶

The rationale for these recommendations is to reduce disease recurrence risk, improve disease survival rates, and reduce comorbid conditions.³ For Latinos living in rural medically underserved regions, meeting these recommendations is hindered due to limited resource availability and sociocultural barriers (linguistic, beliefs). These barriers contribute to poor diet quality, low physical activity (PA), disproportionately high risk of chronic diseases, and poor cancer-related outcomes, compared to non-Latino Whites.^{4, 5} To address these disparities, innovative approaches utilizing effective technologies, culturally appropriate education, and skill building are needed to lay the groundwork for scalable and sustainable interventions.

2.2 Background

[name] has developed and demonstrated feasibility and effectiveness of theory-based multi-strategy (in-person group and electronic e-health communication) interventions to improve nutrition and PA among urban Latino (primarily Dominican and Puerto Rican) cancer survivors (R21CA152903; R01CA186080).⁶⁻⁸ In collaboration with [name] and her community partners in Yakima County, WA, the proposed pilot project will adapt [name] existing *Mi Vida Saludable* (My Healthy Life) intervention to address the sociocultural (cultural, infrastructural, and logistical) needs of rural-dwelling, primarily Mexican-American, Latino adults with a history of hypertension, diabetes, cardiovascular disease, cancer, or obesity and test the feasibility of the adapted intervention. Latino adults with hypertension, diabetes, cardiovascular disease, obesity, and/or a history of cancer (n=25) who live in Yakima County's agricultural region known as the Lower Yakima Valley will be recruited. Participants will receive a high dose intervention delivery.

2.3 Risks/Benefits

There are few potential risks that may occur to participants. There may be some discomfort in completing questionnaires about cancer and other diseases, but staff are trained to be aware of such discomfort and are trained to be compassionate to individuals answering such questions. Research related injuries are highly unlikely due to the low risk nature of this study; however, there is a risk of unintentional injuries that may occur while cooking, dancing or participating in exercises as promoted via online sessions. Participants will be asked to increase their physical activity during the 3 months of the study. This increased physical activity may cause unintentional soreness, joint pain or exercise related injuries. Recommended dietary changes may include gas and bloating due to increased fiber consumption. The timing and frequency of the online sessions and data collection at baseline and 3 months may provide an inconvenience to participants' schedules.

Participants will receive up to \$50 in compensation in the form of a gift card to a local vendor. Since the in-person session are to be delivered via online Zoom videos, we are also providing participants randomized to receiving the online sessions with a grocery bags with an estimated cost of \$25 or less per sessions for total of \$150 in groceries per participant to cover all six sessions or one session. Aside from the gift card and grocery bags and gaining new knowledge about ways in which participants can decrease their risk of cancer reoccurrence by being physically active and consuming a diet high in fruits and vegetables and low in fat and added sugar, there are no other direct benefits of this research to a given study participant. The data from the study will be used to direct future intervention efforts targeting similar populations.

3.0 OVERVIEW OF CLINICAL TRIAL

3.1 Study Objectives

This feasibility study aims to assess assessability, acceptability, adherence, retention, data collection rates, and required adaptations of an online and eHealth intervention as well as to assess changes from baseline to 3 months in food knowledge and health-related physical activity.

3.1.1 Primary Objectives

Assess feasibility of online group sessions and eHealth intervention strategies.

3.1.2 Secondary Objectives

Assess changes from baseline to 3 months in nutrition and physical activity knowledge and preferences

Assess changes in physical activity patterns as assessed via Fitbit data

3.2 Study Population

Our aim is to enroll 25 adult Latinos in the Lower Yakima Valley. Participants must have one or more of the following: hypertension, diabetes, cardiovascular disease, past cancer diagnosis, or obesity. We will recruit with the assistance of our Community Health Educator (CHE) staff who work at the Fred Hutch satellite site, the Center for Community Health Promotion (CCHP) in Sunnyside, WA.

3.3 Study Design

This is a single arm feasibility study to assess a culturally tailored eHealth diet and physical activity program for rural Latino adults with a history of hypertension, diabetes, cardiovascular disease, cancer, and/or obesity in the Lower Yakima Valley.

3.3.1 Primary Endpoints

Accrual rate, adherence (online sessions attendance in intervention arm, text message responses, and use of website), retention (completion of all study assessments), and acceptability (exit interview). Feasibility of intervention delivery for staff within in the rural community context will also be assessed and necessary adaptations from the urban intervention delivery process will be documented.

3.3.2 Secondary Endpoints

Changes from baseline to 3 months in nutrition and physical activity knowledge and preferences

Changes from baseline to 3 months in physical activity patterns as assessed via Fitbit data

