6.0 STUDY PROCEDURES AND INTERVENTION

Figure 1. Study Flow Chart

[figure not shown]

Table 1. Data Collection Overview

MEASURE	Screening	Baseline	Follow-up
		T1	T2
Eligibility criteria	X		
At-home assessments:			
Demographic and clinical characteristics		X	
Self-reported weight		X	X
Dietary Intake and PA measures:			
Social and Behavioral measures:			

Physical Activity Questionnaire		X	X
Psychosocial/Quality of Life Outcomes		X	X
Nutrition and physical activity knowledge and preferences		X	X
Exit Interviews on intervention acceptability			X

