Baseline Data Collection. Eligible participants will undergo remote baseline assessments that will include at-home, over the phone and web-based data collection and a “run-in” within an 8-week period prior to the start of the intervention (see [Figure 1](#)). Reasons for the run-in period include opportunities to: 1) assess participant's ability to complete trial assessments, 2) facilitate building of a rapport between the CHE and participant, and 3) ensure CHEs have the time needed to provide participants with proper orientation to the project and assistance completing surveys and study assessments. Because this pilot project will assess feasibility, this information is essential to determine acceptability of the project protocol.

All data collection materials will be provided to participants in Spanish or English based on the participants preferred language. For participants with low literacy, the CHEs are trained to assist in completing surveys without leading responses. Demographic, clinical characteristics, mediators of behavior change within domains framed within SCT and SDT, psychosocial and quality of life outcomes, stress, and acculturation will be assessed at T1. Details regarding data collection methods for these outcomes can be found in Table 4. Measurement Tools, Data Collection Timing, and Timing of Intervention Activities ([Appendix D](#)). Baseline survey materials are found in [Appendix E](#).

The baseline data collection will include completion of an electronic (e) eConsent form via a secure HIPPA-compliant REDCap interphase and the following assessments: 1) online self-administered questionnaires

assessing demographics, medical history, clinical characteristics and self-reported height and weight; mediators of behavior change; and patient-reported psychosocial and quality of life (QOL) outcomes.

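### The Fitbit endpoint is a change from baseline, but no Fitbit wear before the intervention is required or assigned as that baseline

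*Combined protocol and SAP*

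**What the plan says.** **Endpoint.** Section 3.3.2 lists "Changes from baseline to 3 months in physical activity patterns as assessed via Fitbit data" as one of two secondary endpoints. Section 3.1 applies the same interval to health-related physical activity without naming a device. Section 3.1.2 ("Assess changes in physical activity patterns as assessed via Fitbit data") and the synopsis ("Changes in physical activity patterns as assessed via Fitbit data") name Fitbit without repeating the interval. The device table in Section 6.5 has the Fitbit worn from baseline until the 3-month assessment.

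**Supply of the device.** The design overview in Section 1.0 says: "Following the completion of baseline data collection, participants will receive the intervention. All participants will receive a Fitbit device to self-monitor their PA". In Section 6.1, under Intervention, the coordinator first phones with the start date. A package containing the Fitbit is then mailed, and staff phone again a week after it arrives. Use of the Fitbit is taught in class 1 (Section 6.3, Table 2).

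**Baseline measures.** The itemised baseline collection in Section 6.1 reads "HIPPA-compliant REDCap interphase and the following assessments: 1) online self-administered questionnaires", followed by questionnaire topics only. In Table 1 (Section 6.0) the heading "Dietary Intake and PA measures" has no rows beneath it in the supplied text. No Fitbit row appears at T1 or T2. A Physical Activity Questionnaire is scheduled at both.

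**Data and analysis.** Section 12.0 fetches steps, distance, calories and active time, down to the minute, with weekly downloads until the last visit. Section 13.2 promises descriptive summaries of all endpoints. Section 13 does not mention Fitbit.

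**The concern.** The study has one arm, so each participant's own change is the only Fitbit contrast, and the reference value is half of it. If the device first comes into use around session 1, what gets called baseline is early intervention data. The reported figure would then be a change within the intervention and not a change from before it. Section 1.0 says the pilot is to supply preliminary data for a larger trial, so a mislabelled change could be carried into that design. A reference period has to be arranged before session 1; days that were not worn cannot be recovered afterwards.

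**Working it through.** The plan gives no figure to reproduce for this endpoint: no effect size, standard deviation, alpha or power. The check is therefore mainly a comparison of the sections.

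**1. What the endpoint needs.** For each participant, change = follow-up Fitbit summary − reference Fitbit summary, with the reference taken before the intervention.

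**2. Which sections supply the reference.**

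| Place | What it gives | Secures wear before session 1? |
|---|---|---|
| 3.3.2 | Change anchored to baseline | Requires it, does not arrange it |
| 6.5 | Wear starts at baseline | Points that way; no days assigned |
| 1.0, design overview | Device described after baseline collection, for self-monitoring | No |
| 6.1, baseline list | Questionnaires | No |
| 6.1, run-in purposes | Ability to complete assessments, rapport, orientation and help | Fitbit wear not among them |
| 6.1, Intervention | Device mailed after the start-date call | Possible, not required |
| 6.0, Table 1 | No Fitbit row at T1 or T2 | No |

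Only Section 6.5 points towards a pre-intervention reference, and it does not say which days. Section 6.7 defines follow-up as a repeat of the Table 1 measures, so the 3-month Fitbit window is not fixed either.

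**3. Whether wear before session 1 may happen anyway.** Probably, for some. The staff call a week after the package arrives suggests it is meant to come some time before the first class. Such days would be incidental and would vary between participants.

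**4. Exposure in a late reference.** A window that ends before session 1 contains 0 of 6 sessions. The first 7 days from session 1 contain 1/6 = 16.7% of sessions and, if texts run alongside the classes, 1/12 = 8.3% of text weeks. These are shares of exposure, not of effect.

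**5. Direction.** If activity rises promptly and holds, a late reference is too high and the change is understated. If activity dips at first, the reverse follows. The documents give no basis for choosing between these.

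**6. Reach of a remedy.** Section 1.0 reports 22 recruited against a target of 25 and does not say how many had started. If all had, 25 − 22 = 3 participants could still be given a planned window; if none had, all 25 could. The range is 3 to 25.

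**7. Summary and valid day.** Four data streams are fetched and none is named for this endpoint. Section 12.0 asks for wear while awake and weekly syncing, but no minimum wear defines a usable day. Wear time is not one of the four streams, so it would have to be inferred from the minute-level data.

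**The case against.** The strongest reply is that this is a descriptive secondary outcome in a 25-person feasibility study. Wear is said to start at baseline, the mailing sequence probably leaves some days before class 1, and Figure 1 or Appendix D may set the timing. Table 1 also schedules an activity questionnaire at T1 and T2, so a comparison anchored before the intervention exists without the Fitbit. All of this stands and limits the point. It does not supply a reference: wear that happens to occur is not a defined baseline. The unnamed summary and valid-day rule are, as the reply would say, mostly detail that an analyst would fill in.

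Some stronger readings are not supported:

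- **Conflicting baseline lengths.** A reader might set "Eligible participants will undergo online baseline assessments over a period of 1-2 weeks" against "within an 8-week period prior to the start of the intervention". Assessments lasting one to two weeks fit inside an eight-week period that also holds the run-in. No contradiction is shown, and the shorter figure does not measure the time available for device wear.
- **A percentage bias.** With constant hourly activity and assumed wear falling from 14 to 12 hours a day, the daily total changes by (12 − 14)/14 = −14.3%; the reverse gives (14 − 12)/12 = +16.7%. This shows why non-wear needs a rule. The hours are assumptions, and the result does not measure the bias from an undefined reference.
- **Dropping the baseline anchor.** Section 3.3.2 could be reworded to match the unanchored versions, but Section 3.1 would then still promise a change from baseline in physical activity.

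**Conclusion.** The point holds for the text available. The endpoint calls for change from baseline, and following the plan as written does not secure a Fitbit value from before the intervention. The bias has no derivable size or direction. It would be wrong to infer that no participant will have such data, or that the endpoint cannot be analysed; what is missing is a requirement and an assigned window.

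The consequence is limited to one of two secondary endpoints, reported descriptively. The primary feasibility endpoints are unaffected. The conclusion assumes that Figure 1 and Appendix D do not fix a Fitbit reference window. If either does, the main part of the point falls away, leaving the summary and valid-day rule still to be added to Section 13.2. It is worth correcting before analysis.

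**What to change.** 1. Reconcile Section 1.0, Table 1 and Section 6.1 with Section 6.5 on when the device is supplied and when wear begins. Add a Fitbit row to Table 1 at T1 and T2.
2. For participants not yet started, mail the existing package early enough in the run-in to give a fixed window before session 1, for example 7 days, and use it as the reference. Use the last 7 days before T2 as follow-up, drawn from the weekly downloads already planned. The session and text schedules stay as they are.
3. For participants already started, use any wear days before session 1 as the reference. Where there are none, report change over the wear period separately and do not label it change from baseline.
4. In Section 13.2, name the summary (for example mean steps per valid day) and define a valid day from the minute-level data. Do not score non-wear as zero. Report how many participants have a valid pre-session reference.

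**Cost.** Wording in four places, some processing to infer wear, and slightly earlier mailing. The reference window would be unmasked: participants see their counts, so any immediate effect of the display is already in it, and wear would precede the class 1 teaching. Some participants will have no valid reference. The earlier mailing may reach as few as 3 people. Time is short as well: listed funding ends on December 31, 2021, 74 days after this version (13 + 30 + 31), while the text programme alone lasts 12 × 7 = 84 days. The window should therefore use the existing run-in and not lengthen it.
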